12.1 Variables and derivations

The date of first treatment administration will be derived as the first date of dosing from the exposure eCRF page.

The following parameters will be presented for the exposure summary:

- Number of subjects received first dose
- Number of subjects received weekly doses by each visit
- *Duration of exposure (days) =*
(Date of last treatment administration - Date of first treatment administration) + 1

Compliance will be calculated as follows:

- Compliance with the study treatment (%) = (Actual Dose/ Planned Dose)*100

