14.2 Analysis

Population: SAF and PP

Stratification: Table: Add the strata as needed in case subjects with dose modification exceeding 20% based on enrolled population as per section 7.3:

a. Subjects on 1.5 mg only by ATC and PT

b. Subjects on 0.75 mg only by ATC and PT

c. Subjects with any dose modification* by ATC and PT

* Subjects who have received at least one dose of 1.5 mg and at least one dose of 0.75 mg

Listing: By subject

Statistics: Prior and concomitant medication will be summarized separately as (frequency, percentages) for table and listing will be presented.

15. Adverse events**15.1 Variables and derivations**

Adverse Events (AEs) will be coded using MedDRA central coding dictionary, Version (refer to DMP for dictionary version).

For the definition of Adverse events (AE) and Serious adverse event (SAE) refer to the protocol section 10.3.

TEAEs are defined as events that are newly reported after the first study drug treatment or are reported to have worsened in severity after the first study drug treatment.

In section 24 Appendix 2 the algorithm is given for calculation of partial date imputation for adverse events (AEs), and it will be used for partially missing adverse event start and end date imputation.

The following parameters will be summarised for the overview of participants' adverse events:

- Any AEs
- Any TEAEs
- Related TEAEs
- Severity of TEAEs (Mild, Moderate, Severe, Life threatening and Death)
- Outcome of AEs (Recovered or resolved, Recovering, or resolving, Not recovered or not resolved, Recovered, or resolved with sequelae, Fatal and Unknown)
- Serious AEs
- AEs leading to Discontinuation from the study
- AEs leading to Death
- Related AEs leading to Death

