17.2 Analysis

Population: SAF and PP

Stratification: Table: Add the strata as needed in case subjects with dose modification exceeding 20% based on enrolled population as per section 7.3:

- a. Subjects on 1.5 mg only
- b. Subjects on 0.75 mg only
- c. Subjects with any dose modification*

* Subjects who have received at least one dose of 1.5 mg and at least one dose of 0.75 mg

Listing: by subject, visit and each vital sign parameter

Statistics: The vital signs except temperature will be summarised as actual and change from baseline (number of patients, mean, SD, median, minimum, maximum, and interquartile ranges) for table. The listing will be presented for all vital sign parameters. Mean \pm SD plot will be provided for Vital sign parameters.

18. Primary endpoint**18.1 Incidence of AEs (deaths, SAEs, TEAEs, and hypoglycemia, including severe hypoglycemia)****18.1.1 Variables and derivations**

Variables:

- All AEs will be captured in the “Adverse Events” eCRF form.
- Hypoglycemia events will be captured in the “Hypoglycemic events” eCRF form.

Derivations:

- To identify incidence of deaths the eCRF question “the severity of the adverse event” = “Death” will be used from AE form.
- If the question “the adverse event serious” is indicated as “Yes” then corresponding events will be considered as SAEs.
- If the AE started on or after the first treatment administration date will be considered as TEAEs.
- Hypoglycemia events will be captured and identified using the “Hypoglycemic events” eCRF form.
- If the question “Did subject have any Hypoglycemic events” is “Yes” on “Hypoglycemic events” eCRF form and the question “the adverse event serious” is indicated as “Yes” on the AE eCRF form, then corresponding events will be considered as severe hypoglycemia events.
- The incidence of AEs= Number of new AEs post intervention/Total eligible population *100.
- The incidence of hypoglycemic AEs= (Number of new hypoglycemic AEs post intervention/Total eligible population)*100.
- Number of hypoglycemic events per patient-year (365.25 days)= Number of patients with hypoglycemic events /365.25
- Exposure Adjusted AE Incidence= Number of patients with new or worsened AEs during treatment period / (Patient-year exposure/365.25)
- Patient-year exposure is counted in days up to the AE (or end of time at risk for subjects without AE).

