18.1.2 Analyses

Population: FAS and PP

Stratification: Table: Add the strata as needed in case subjects with dose modification exceeding 20% based on enrolled population as per section 7.3:

- a. Subjects on 1.5 mg only
- b. Subjects on 0.75 mg only
- c. Subjects with any dose modification*

* Subjects who have received at least one dose of 1.5 mg and at least one dose of 0.75 mg

Listing: by subject and events

Statistics: The incidence of AEs (including deaths, SAEs, TEAEs, hypoglycemia, including severe hypoglycemia and GI disorders) will be summarised as frequency and percentages.

The listings will be presented for the hypoglycaemia events.

The incidence of AE (death, SAE, and TEAE) will be summarized. The rate per year (i.e., number of deaths, SAE, and TEAEs per subject per year over the study period) will be assessed using a negative binomial model with the log of the study treatment exposure time as an offset variable and the model will be performed as per details mentioned below.

The incidence of hypoglycemic AEs will be summarized. The number of hypoglycemic events per subject over the study period will be analysed as continuous variables and will be summarized as (n, mean, standard deviation, standard error, median, minimum, maximum).

The rate per year of hypoglycemic events, that is, the number of hypoglycemic events per patient-year (365.25 days) will be assessed using a negative binomial model, with baseline HbA1c and baseline insulin usage as covariates and the log of the study treatment exposure time as an offset variable.

The Negative Binomial Model i.e., the generalized linear model will be used with baseline HbA1c and baseline insulin usage and the log of the study treatment exposure time as offset variable.

The incidence rate, least square mean and corresponding 95% confidence interval will be provided for table.

Also, in case we have more than 20% data missing in any of the covariate, we will repeat the analysis after omitting the impacted covariate.

In case of multiple doses of insulin uptake per day, a sum of insulin per day will be used as the baseline insulin covariate. Regimen for subjects with more than 1 regimen type per day will be reviewed by

medical team. Insulin Dose level for subjects not on insulin will be considered as 0 and the corresponding regimen as 'Non'.

In case convergence is not met with the above variables, only baseline HbA1c and baseline insulin usage(Yes/No) will be considered.

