18.2.1 Variables and derivations

Variables:

- All AEs and SAEs will be captured in the "Adverse Events" eCRF form.

Derivations:

- AE and SAE occurred between visit Baseline Visit 2 (week 0) and Visit 8 (week 24) will be used.

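### The modelled yearly AE and hypoglycemia rates use treatment exposure time as offset, but no rule ties the counted events and that offset to the same window

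*SAP*

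**What the plan says.** **The model.** SAP 18.1.2 defines the AE rate as the "number of deaths, SAE, and TEAEs per subject per year over the study period". It "will be assessed using a negative binomial model with the log of the study treatment exposure time as an offset variable". The hypoglycemia rate uses the same offset, with baseline HbA1c and baseline insulin use as covariates. Protocol 9.4.2 names the same offset for both. Neither document defines the study period for these rates.

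**Which events count.**
- SAP 15.1: "TEAEs are defined as events that are newly reported after the first study drug treatment", or that worsen after it. No end date is given.
- SAP 18.1.1: "If the AE started on or after the first treatment administration date will be considered as TEAEs". Again there is no end date.
- SAP 18.1.1 identifies SAEs by the seriousness item on the form ("then corresponding events will be considered as SAEs"), with no dates in that rule.
- The protocol's glossary (10.7) instead ties a TEAE to a defined treatment period.
- Protocol 8.3.1 collects AEs and SAEs to the last safety follow-up visit, which the schedule puts at Week 28. Protocol 7.1 keeps patients who stop drug permanently in the study for the remaining visits.

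**Which exposure time.** Two definitions are available, and 18.1.2 refers to neither.
- SAP 12.1, for the exposure summary: "Date of last treatment administration - Date of first treatment administration) + 1".
- SAP 18.1.1, for exposure-adjusted incidence: days up to the AE, or to the end of time at risk in patients without one.

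**The concern.** A rate model with a log-time offset estimates events per unit of time only if the events come from the time in the offset. Here the count can run past the last injection while the offset may stop there. Each later event then raises the rate with no time to balance it. Patients who stop early and stay on study are the clearest case: their offset is short and they still contribute events.

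These rates and their 95% confidence intervals are reported under the primary safety endpoint and repeated in every subgroup. Two programmers following the SAP could choose different windows or offsets and report different rates from the same data.

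**Working it through.** The documents give no AE or hypoglycemia rate, so there is no planned figure to reproduce. The check asks how far the rate moves if the SAP 12.1 duration is the offset.

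**Inputs from the documents.** Once-weekly dosing (protocol 6.1); the SAP 12.1 formula; Visit 8 at Week 24 and Visit 801 at Week 28 (SAP 23.9); 200 patients starting drug (protocol 9.6).

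**Assumptions.** The number of doses, the share who stop drug but stay on study, and the event rate after the last dose are not given, so ranges are shown. A last dose at Week 24 (25 doses) fits the synopsis best, because follow-up is 4 weeks after the last treatment and falls at Week 28. A last dose at Week 23 (24 doses) is shown as well.

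**Step 1: days, counted inclusively.**
- Exposure by SAP 12.1: 25 doses, (25 − 1) × 7 + 1 = 169; 24 doses, (24 − 1) × 7 + 1 = 162.
- Observation: Week 24, 24 × 7 + 1 = 169; Week 28, 28 × 7 + 1 = 197.

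**Step 2: completers, constant event rate.** Ratio = counting days / exposure days.

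| Counted to | 25 doses | 24 doses |
|---|---|---|
| Week 24 | 169/169 = 1.000 | 169/162 = 1.043 |
| Week 28 | 197/169 = 1.166 | 197/162 = 1.216 |

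**Step 3: 10% stop drug, spread evenly over the schedule, all followed (illustration).** Mean exposure of those who stop is 81.5 days (25 doses) or 78 days (24 doses).
- Total exposure, 25 doses: 180 × 169 + 20 × 81.5 = 32,050 days. 24 doses: 180 × 162 + 20 × 78 = 30,720 days.
- Counted to Week 24 (200 × 169 = 33,800 days): 33,800/32,050 = 1.055 and 33,800/30,720 = 1.100.
- Counted to Week 28 (200 × 197 = 39,400 days): 1.229 and 1.283.

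**Step 4: lower event rate after the last dose.** If the post-dose rate is a fraction f of the on-treatment rate, the ratio becomes 1 + f × (constant-rate ratio − 1).

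| Case | 25 doses, f = 0.25 / 0.50 | 24 doses, f = 0.25 / 0.50 |
|---|---|---|
| Week 24, 10% stop | 1.014 / 1.027 | 1.025 / 1.050 |
| Week 28, completers | 1.041 / 1.083 | 1.054 / 1.108 |

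**Step 5: the fitted model.** I simulated 300 trials of 200 patients (true rate 2.0 per year, dispersion 1, no covariates, 10% stopping evenly, counted to Week 24; Monte Carlo error of the ratio about 0.007).
- Constant rate: fitted-to-true ratio about 1.09 (25 doses) and 1.13 to 1.14 (24 doses).
- f = 0.50: 1.03 to 1.05 (25 doses) and about 1.07 (24 doses).
- If nobody stops before dose 13 (25 doses, constant rate), 1.09 falls to 1.03.

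The excess over the person-time ratio arises because the model gives patients with short exposure more weight, so it depends on how early patients stop.

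**Step 6: matched windows.** In a similar simulation with events counted to Week 28, restricting events to the exposure interval, or using observation time as the offset for all events, returned 1.99 to 2.00 against a true 2.0.

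**The case against.** The strongest reply is that the text, read as a whole, points to Week 24 and to time at risk.
- Protocol 10.7 limits TEAEs to a defined treatment period.
- Protocol 9.4.2 equates the study's duration with 24 weeks when it describes the proportions. SAP 18.2.1 says "AE and SAE occurred between visit Baseline Visit 2 (week 0) and Visit 8 (week 24) will be used".
- SAP 18.1.1 states exposure-adjusted incidence as "Number of patients with new or worsened AEs during treatment period" over exposure, and in that same section counts exposure as time at risk.
- SAP 12.1 offers its formula only for the exposure summary.
- There is no hypothesis, comparator or rate threshold.

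Most of this stands as evidence of intent. A reader might infer that the reported rates will be 17% to 28% too high. The documents do not support that: it needs the 12.1 offset, a Week 28 count and a constant event rate together, and protocol 4.2 says the most common side effects occur early. Nor do the Week 28 figures carry over to diary-recorded hypoglycemia, because the schedule marks diary collection only through Visit 8. A reader might also infer that SAEs from before treatment enter the rate, since the SAE rule has no dates. The same list defines incidence by new events after the intervention, and SAP 15.2 lists pre-treatment AEs separately, so that inference is weak.

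The reply does not close the gap. The Week 24 wording belongs to the proportions, and the time-at-risk sentence to a different statistic; counting time only up to the AE does not suit a model of repeated events. The TEAE definitions in SAP 15.1 and 18.1.1 remain open-ended against protocol 10.7. A Week 24 limit still leaves unmatched events in patients who stop early and stay on study. The full analysis set used in 18.1.2 keeps those who have a later HbA1c. The per-protocol repeat does not have this early-stopper bias, because that set requires completion of the 24-week treatment phase.

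**Conclusion.** The point holds as a conditional one. The SAP does not set a counting window for these rates or identify the offset variable, and its TEAE rules are not reconciled with protocol 10.7. If the SAP 12.1 duration is used, any counted event after the last injection biases the rate upward. If a matched time at risk is used, there is no such bias.

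On the 12.1 reading with the favoured Week 24 count, the size is 0% to 4% for completers. With 10% stopping and staying on study it is about 1% to 5% at 25% to 50% of the on-treatment event rate, and 5% to 10% at a constant rate, before the somewhat larger excess in the fitted model. The 17% to 22% for completers under a Week 28 count is an upper bound. The stopping share, its timing and the post-dose rate are assumptions, and the calculation uses the 200 patients starting drug, not the full analysis set.

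Only descriptive, model-based rates are affected. This should be corrected before database lock; it does not threaten the trial's main safety description.

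**What to change.** In SAP 18.1.2, state one window and use it for both the events and the offset. Either:

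1. Count from first dose through last dose plus a stated number of days that covers the weekly dosing interval, cut at withdrawal or death, and use the log of that same time. This stays closest to the protocol's offset.
2. Count from first dose to the end of event collection, withdrawal or death (for hypoglycemia, to the last diary collection), and use the log of that observation time.

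Apply the same start and end dates to the TEAE, SAE, death and hypoglycemia counts in this model. Say whether the SAP 12.1 duration is the offset, reconcile the TEAE definitions in SAP 15.1 and 18.1.1 with protocol 10.7, and record any change from protocol 9.4.2 in SAP section 5.

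The cost is a few SAP sentences and one derived variable from dates already collected. Rates may be somewhat lower than they would have been if the 12.1 duration had been used. Under option 1, later events leave the rate but stay in the counts and listings.

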5.1. Inclusion Criteria

Participants are eligible to be included in the study only if all the following criteria apply:

Age

1. Participants are 18 years of age or older, at the time of signing the informed consent.

Type of Participant and Disease Characteristics

2. Participants have a diagnosis of T2DM for at least 1 year, currently treated with stable doses of oral antihyperglycemic medications with or without stable doses of basal or premix insulin for the last 3 months prior to screening. Premix insulin is allowed up to twice daily in the screening period to be taken up further. Doses of other OHAs will be optimized as per investigator's discretion. Patients on thrice-daily premix insulin or full basal bolus insulin (insulin regimen, 3 to 4 times daily) therapy are excluded from the study.
3. Participants have HbA1c $\geq 7.5\%$ and $\leq 11.5\%$, both inclusive, at screening.

Weight/BMI

4. Participants have BMI $\geq 23 \text{ kg/m}^2$.

Sex and Contraceptive/Barrier Requirements

Contraceptive use by participants should be consistent with local regulations regarding the methods of contraception for those participating in clinical studies.

5. Male study participants: No male contraception is required except in compliance with specific local government study requirements. Female study participants: For the contraception requirements of this protocol, see Section 10.4.

Informed Consent

6. Participants are capable of giving signed informed consent as described in Appendix 1, which includes compliance with the requirements and restrictions listed in the ICF and in this protocol.

Other Inclusions

7. Residents of India

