9.4.2. Primary Endpoints Analysis

AEs (deaths, SAEs, TEAEs, and hypoglycemia, including severe hypoglycemia)

Frequency and percentage of AE occurrence (including deaths, SAEs, TEAEs, hypoglycemia, including severe hypoglycemia and GI disorders) will be presented for the study duration using safety population.

The proportion of patients with AEs and SAEs occurring within the duration of the study (24 weeks) after being administered dulaglutide 1.5 or 0.75 mg will be presented.

The proportion of patients with AEs, TEAEs, and SAEs occurring within the duration of the study (24 weeks) after being administered dulaglutide 1.5 or 0.75 mg and 95% CIs will be estimated based on normal approximation.

The incidence of AE (death, SAE, and TEAE) will be summarized. The rate per year will be assessed using a negative binomial model with the log of the study treatment exposure time as an offset variable.

The incidence of hypoglycemic AEs will be summarized. The number of hypoglycemic events per subject over the study period will be analyzed as continuous variables and will be summarized (mean, median, SD, SE, minimum, and maximum).

The rate per year of hypoglycemic events, that is, the number of hypoglycemic events per patient-year (365.25 days) will be assessed using a negative binomial model, with baseline HbA1c and baseline insulin usage as covariates and the log of the study treatment exposure time as an offset variable.

The incidence of AEs will be calculated based on the number of new AEs out of the total eligible population using the following formula:

$$\text{Number of new AEs post intervention/Total eligible population *100.}$$

Exposure-adjusted AE incidence will be presented by the severity and preferred term for the primary analysis.

It is defined as

Number of patients with new or worsened AEs during treatment period

Patient-year exposure/365.25

Patient-year exposure is counted in days up to the AE (or end of time at risk for subjects without AE).

Incidence of gastrointestinal AEs

The incidence of GI AEs per week will be plotted over time from baseline up to 24 weeks. The proportion of subjects with at least 1 GI AE will be plotted from baseline up to Week 24. A plot of prevalence by severity (mild, moderate, or severe) for nausea, vomiting, and diarrhea over the 24-week period will be provided for the rate of GI AEs.

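### SAP 18.1.2 tables the yearly AE and hypoglycemia rates with a covariate-adjusted least-squares mean that is not the rate in the treated patients, and it defines no crude event rate beside it

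*SAP*

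**What the plan says.** Protocol 9.4.2 treats the two rates differently. For deaths, SAEs and TEAEs: "The rate per year will be assessed using a negative binomial model with the log of the study treatment exposure time as an offset variable". No covariates are named. For hypoglycemia the same kind of model is used, but "with baseline HbA1c and baseline insulin usage as covariates".

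SAP 18.1.2 merges them. After introducing the AE rate model with its offset, it adds that "the model will be performed as per details mentioned below". The details that follow are: "The Negative Binomial Model i.e., the generalized linear model will be used with baseline HbA1c and baseline insulin usage", with log exposure as offset. Insulin enters first as total daily dose and regimen: "Insulin Dose level for subjects not on insulin will be considered as 0 and the corresponding regimen as" a level called Non. A plain yes/no indicator is the fallback if the model does not converge. The output is then set: "The incidence rate, least square mean and corresponding 95% confidence interval will be provided for table".

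SAP 18.1.1 has three related formulas. AE incidence is new AEs over eligible patients, times 100, with no time element. Hypoglycemic events per patient-year is the number of patients with events divided by 365.25. Exposure-adjusted AE incidence is patients with new or worsened AEs over exposure in years. SAP section 5 states that nothing has changed from the planned analyses.

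**The concern.** The primary objective is descriptive: how often do the treated patients have these events? With a log link, an LS mean averages on the log scale at chosen covariate values. Back-transformed, it gives the rate for a reference covariate profile. In a randomized trial this largely cancels in a rate ratio between arms. Here there is no second arm, and the absolute rate is what gets reported.

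The eligibility criteria admit patients "with or without stable doses of basal or premix insulin", so insulin users and non-users will be mixed in a proportion the plan does not predict. If their event rates differ, the LS mean and its 95% CI need not agree with events divided by patient-years. A reader of the report could take one for the other. For deaths, SAEs and TEAEs the covariates are also an undeclared departure from the protocol.

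**Working it through.** **The plan's own figures.** The only planning numbers are in Protocol 9.6: 250 × (1 - 0.20) = 200 treated, and 200 × (1 - 0.20) = 160 completers. Both reproduce. The documents give no event rate, insulin share or insulin rate ratio, so everything below is an assumption shown over a range.

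**Formulas.** Take a yes/no insulin factor and the LS mean back-transformed to the rate scale. Let p be the share on insulin, r0 the rate off insulin, and R the rate ratio, insulin versus none.

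- Rate in the treated patients: r0 × [(1 - p) + pR]
- LS mean, equal weights on the two levels: r0 × √R
- LS mean, observed-share weights: r0 × R^p

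The ratios of LS mean to treated-patient rate are therefore √R / [(1 - p) + pR] and R^p / [(1 - p) + pR].

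**Worked case, R = 3.** At p = 0.2, equal weights give 1.732 / 1.4 = 1.24. At p = 0.5 they give 1.732 / 2 = 0.87. Observed weights are lowest near p = 0.4: 3^0.4 / 1.8 = 1.552 / 1.8 = 0.86.

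**Range (equal weights / observed weights).**

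| R | p = 0.1 | p = 0.2 | p = 0.3 | p = 0.5 | p = 0.7 |
|---|---|---|---|---|---|
| 1.25 | 1.09 / 1.00 | 1.06 / 1.00 | 1.04 / 0.99 | 0.99 / 0.99 | 0.95 / 0.99 |
| 2 | 1.29 / 0.97 | 1.18 / 0.96 | 1.09 / 0.95 | 0.94 / 0.94 | 0.83 / 0.96 |
| 3 | 1.44 / 0.93 | 1.24 / 0.89 | 1.08 / 0.87 | 0.87 / 0.87 | 0.72 / 0.90 |

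At R = 1 every ratio is 1. Observed weights never give a ratio above 1.

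**Coding matters.** If regimen has three equally weighted levels (none, basal, premix), both insulin regimens share R, and the dose term is ignored, the equal-weight ratio is R^(2/3) / [(1 - p) + pR]. At p = 0.2 this is 1.160 / 1.05 = 1.11 for R = 1.25, 1.32 for R = 2 and 1.49 for R = 3. With dose also in the model and held at its mean, the Non level is evaluated at a non-zero insulin dose, a patient who does not exist.

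**HbA1c.** Evaluating at mean HbA1c multiplies the result by exp(-b²·SD²/2) under normality, where b is the log rate ratio per 1%. For SD 0.8 to 1.15 and rate ratios per 1% of 0.6 to 0.8 or 1.25 to 1.5, the factor is 0.84 to 0.98.

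**Simulation check.** Settings: 200 patients, 20% early dropout with shorter exposure, 2 events per year off insulin, dispersion 2, 400 trials per setting. The median ratio of the equal-weight LS mean to the true rate was 1.38 (R = 3, p = 0.1), 1.04 (R = 3, p = 0.3), 0.70 (R = 3, p = 0.7) and 1.02 (R = 1.25, p = 0.3). Crude events per patient-year, the offset-only model and the marginal rate from the covariate model all had medians of 0.98 to 1.01 in every setting.

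**The case against.** The strongest reply is that the SAP sentence lists an incidence rate as well as an LS mean. A reader might infer that the LS mean is the only rate to be reported, and the text does not establish that. This part of the reply stands. But the sentence attaches one CI, does not say whether the two quantities differ, and has no valid definition to fall back on. The per-patient-year formula in SAP 18.1.1 has neither an event count nor an exposure denominator, and the exposure-adjusted incidence counts patients, not events.

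A reader might also infer errors as large as 30% too low or 40% too high. The documents do not support that. With R = 3 and equal weights, +40% needs about 12% insulin users (1.732 / 1.4 = 1 + 2p) and -30% needs about 74% (1.732 / 0.7 = 1 + 2p). One trial cannot have both, and observed weights rule out any overstatement. Nothing in the documents suggests a large insulin effect on all AEs, SAEs or deaths.

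Three further replies stand. Yes/no coding is the SAP's fallback, so the main figures illustrate the problem and do not predict the first-choice model. The weights may be set in the separate output templates, which are not available. The hypoglycemia covariates come from the protocol, so removing them there would itself be a departure.

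The rule for when "in case we have more than 20% data missing in any of the covariate" might suggest that many patients drop out of the model. That is unlikely. Baseline is the last non-missing pre-dose value, HbA1c is an entry criterion drawn at screening and Visit 2, and non-users have dose 0.

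Finally, frequencies, percentages and mean hypoglycemic events per subject are also planned, and Protocol 9.1 has no hypothesis. This lowers the stakes but supplies no event rate per year with a CI.

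**Conclusion.** The point holds as a should-fix. The plan tables a conditional LS mean, with unstated weights, beside an undefined incidence rate, in a trial whose primary result is an absolute rate. It also adds covariates to the death, SAE and TEAE rate model without declaring the change from the protocol.

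Both the size and the direction of the gap depend on the insulin coding, the LS-mean weights, the insulin share and the insulin rate ratio. The documents settle none of the last three, and they leave the coding to convergence. Under yes/no coding with an assumed rate ratio of 3, the gap is about +24% at 20% users and -13% at 50% users with equal weights, and at most about -14% with observed weights. For all AEs, an assumed ratio of 1 to 1.25 gives 0 to about 10% from the insulin term under the same coding. The case is therefore strongest for hypoglycemia. For the AE rates it rests mainly on the mismatch with the protocol and the missing definition.

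**What to change.** In SAP 18.1.2, before database lock:

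- Define the headline rate as total events divided by total patient-years.
- For deaths, SAEs and TEAEs, take the 95% CI from the offset-only negative binomial model, as in Protocol 9.4.2.
- For hypoglycemia, keep the protocol's covariates but report the marginal rate: each patient's predicted yearly rate, averaged over the treated patients (the safety analysis set, which Protocol 9.3 assigns to safety endpoints), with a delta-method or bootstrap 95% CI.
- Show the HbA1c and insulin effects as rate ratios. If an LS mean is kept, label it as conditional and state its weights and covariate values.
- In SAP 18.1.1, correct the hypoglycemia formula to events divided by total patient-years.

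The cost is SAP wording and a small amount of extra programming for the marginal rate and its interval. Data collection and patients are not affected.
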